Between screening and the last visit, subjects will attend a total of 14 planned visits. Unscheduled visits are permitted at the Investigator's discretion.

A schematic representing the study's design is included below:

Progression from Cohort 1 to Cohort 2

Approximately 12 weeks after the 9th subject in Cohort 1 has been randomized, blinded safety data will be reviewed by the Sponsor Study Review Committee (SSRC). Members of this committee will include a Sponsor medical representative, the Medical Monitor and the study's Principal Investigator. Cohort 2 will be opened for screening once the following criteria have been met:

1. All 12 subjects from Cohort 1 have been randomized,

2. No significant safety issues related to the administration of MAU868 have been identified by the SSRC based on the blinded safety review described above as well as an assessment of any new SAEs reported after the SSRC review and before randomization of the 12th subject in Cohort 1.
3. No significant safety issues related to the administration of MAU868 have been identified by the independent Data Safety Monitoring Board (DSMB) (see below).

The Chair of the DSMB will be notified of the SSRC's decision to open Cohort 2.

Accordingly, some subjects enrolled in Cohort 1 will continue participation in the study through the 24-week follow-up period while new subjects are screened and enrolled into Cohort 2.

Progression from Cohort 2 to Cohort 3

Cohort 3 will not be opened for screening and enrollment until an evaluation of unblinded safety, efficacy and pharmacokinetics findings from both Cohorts 1 and 2 through the 12-week treatment period has been completed by the SSRC.

DOSAGE FORMS AND DOSE REGIMEN:

The following treatment arms and dosing regimens are planned.

Treatment Arms:

- Cohort 1: MAU868 1350 mg IV approximately every 28 days for a total of 4 doses
- Cohort 2: MAU868 6750 mg IV on Study Day 1 and then 1350 mg IV approximately every 28 days for a total of 4 doses
- Cohort 3: MAU868 6750 mg IV approximately every 28 days for a total of 4 doses

Cohorts 1, 2, and 3 Placebo Arms:

- 5% dextrose in water [D5W] IV delivered every 28 days for a total of 4 doses

MAU868

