An independent data safety monitoring board (DSMB) will review cumulative unblinded safety data as outlined in the DSMB charter.

STATISTICAL CONSIDERATIONS:

Analysis Populations:

The primary efficacy analysis will be performed in the modified ITT (MITT) analysis population. The MITT includes subjects who meet all of the following criteria:

- Received at least 1 dose of study drug
- Has at least 1 post-baseline plasma BK viral load result available

Additional analyses will be performed in the Intent-To-Treat (ITT) analysis population (all subjects randomized).

The safety population will include all subjects who received at least 1 dose of study drug.

The PK population will include all subjects with at least 1 post-baseline PK sample available.

Efficacy Analyses

In all efficacy analyses, the placebo subjects from the cohorts will be combined. Thus, the analysis models will include treatment group (four levels: placebo, low dose, medium dose, high dose) as a factor. Time-to-event endpoints will be analyzed using Cox proportional hazards regression models. Proportion endpoints will be analyzed using logistic regression models. Quantitative endpoints will be analyzed using one-way analysis of variance (ANOVA) models. In all analyses, pairwise contrasts comparing each of the three active groups to the combined placebo group will be tested. All efficacy and exploratory analyses will be conducted using two-sided tests at the alpha=0.05 level of significance, with no adjustment for multiplicity.

Additional efficacy analyses will be conducted using the data from each cohort. Quantitative endpoints will be analysed using the two-sample t test and proportion endpoints will be analysed using Fisher's exact test. Due to the small sample sizes, time-to-event variables will be summarized descriptively.

Safety Analyses

All safety analyses will be performed on data from the Safety Analysis Population. Adverse events (AEs), vital signs, ECGs and clinical laboratory evaluations will be summarized by appropriate descriptive statistics.

Pharmacokinetic Analysis

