Routine post-transplantation care is to be guided by the Investigator discretion and site standard of care. This includes decisions to change the immunosuppressive regimen for a subject for any reason except for changes in immunosuppression in response to BK viremia. In order to treat BK viremia, prior to randomization, (ie, prior to screening, during the screening period and at the Baseline Visit) Investigators are permitted to decrease or alter immunosuppressive therapy per their discretion and/or per standard of care at their site. However, in the first 4 weeks after randomization, Investigators should refrain from additional changes in immunosuppressive regimen in response to BKV unless the viral load has increased by ≥ 1 log and the Investigator determines that a change is in the best interest of the subject. Use of other antiviral agents including cidofovir and leflunomide as well as IVIG are not permitted during the first 4 weeks of therapy and are strongly discouraged thereafter. Use of fluoroquinolones for reasons other than treatment of BKV is permitted.

Between screening and the last visit, subjects will attend a total of 14 visits.

A schematic representing the study's design is included below:

Progression from Cohort 1 to Cohort 2

Approximately 12 weeks after the 9th subject in Cohort 1 has been randomized, blinded safety data will be reviewed by the SSRC. Members of this committee will include a Sponsor medical representative, the Medical Monitor and the study's Principal Investigator. Cohort 2 will be opened for screening once the following criteria have been met:

1. All 12 subjects from Cohort 1 have been randomized,
2. No significant safety issues related to the administration of MAU868 have been identified by the SSRC based the blinded safety review described above as well as an assessment of any new SAEs reported after the SSRC review and before randomization of the 12th subject in Cohort 1.
3. No significant safety issues related to the administration of MAU868 have been identified by the independent DSMB.

The Chair of the DSMB will be notified of the SSRC's decision to open Cohort 2.

Accordingly, some subjects enrolled in Cohort 1 will continue participation in the study through the 24-week follow-up period while new subjects are screened and enrolled into Cohort 2.

Progression from Cohort 2 to Cohort 3

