4 DATA SAFETY MONITORING BOARD (DSMB)

An independent DSMB will review cumulative unblinded safety data as outlined in the DSMB charter. The DSMB will advise the Sponsor on the continuing safety of the study patients and those yet to be recruited to the study, as well as the continuing validity and scientific merit of the study. At any time, the DSMB may temporarily suspend enrollment until any significant safety concerns are resolved or terminate the study to ensure patient safety, if in the opinion of the DSMB, further dosing would pose an inappropriate safety risk.

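### The SSRC's SAE update for opening Cohort 2 stops at randomisation of the 12th Cohort 1 subject, so SAEs reported between then (or the review, if later) and the opening need no SSRC assessment

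*Protocol*

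**What the plan says.** The Protocol sets out the move from Cohort 1 to Cohort 2 in the Synopsis and again in section 3.1, under the same subheading.

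- **Review.** "Approximately 12 weeks after the 9th subject in Cohort 1 has been randomized, blinded safety data will be reviewed" by the SSRC.
- **Criterion 1.** "All 12 subjects from Cohort 1 have been randomized".
- **Criterion 2.** The SSRC has found no significant MAU868-related safety issue in that review, nor in an assessment of "any new SAEs reported after the SSRC review and before randomization of the 12th subject in Cohort 1".
- **Criterion 3.** The independent DSMB has identified no such issue. The DSMB "will review cumulative unblinded safety data as outlined in the DSMB charter" (Synopsis and section 9.7).
- **After the decision.** "The Chair of the DSMB will be notified of the SSRC's decision to open Cohort 2".

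When all three criteria are met, Cohort 2 opens for screening. Its first active dose is 6750 mg, against 1350 mg in Cohort 1. SAP section 5 repeats the timing of the blinded review but gives neither the criteria nor the SAE update. Protocol section 3.3.3 and SAP section 5 allow a cohort to be expanded beyond 12 subjects.

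**The concern.** The sponsor evidently accepts that the blinded review may have aged by the time Cohort 2 opens, since criterion 2 adds an SAE update. The natural end of such an update is the event it protects, which is the opening of Cohort 2. Criterion 2 ends it instead at randomisation of the 12th subject. That date need not be close to the opening: criterion 3 can hold the opening back, and the documents state no maximum interval. If Cohort 1 is expanded, the window still closes at subject 12.

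Cohort 1 subjects are still being dosed or followed during this time. An SAE among them could be reported after the window has closed and before the opening, and criterion 2 would not require the SSRC to look at it. The decision at stake is the step to a first dose five times the Cohort 1 dose (6750 / 1350 = 5) in a population that, according to Protocol section 1.8, has not been exposed to MAU868 before.

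**Working it through.** The documents give no figure for this interval, so there is none to reproduce. The check has two parts: the timeline the criteria imply, and an illustration of what could fall outside them.

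**1. Timeline.** Set week 0 at randomisation of subject 9. Let R be the review and T12 the randomisation of subject 12.

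- From the Protocol, R is about week 12.
- Length of the SAE window = max(0, T12 − R).
- Earliest opening under criteria 1 and 2 = max(R, T12).
- SSRC coverage of SAEs ends at R if T12 ≤ R, and at T12 otherwise. Both cases equal max(R, T12), taking the review to be current to its own date.

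| T12 (week) | SAE window (weeks) | Earliest opening (week) | SAE coverage ends (week) | Gap to earliest opening (weeks) |
|---|---|---|---|---|
| 3, 6, 9 or 12 | 0 | 12 | 12 | 0 |
| 15 | 3 | 15 | 15 | 0 |
| 18 | 6 | 18 | 18 | 0 |
| 24 | 12 | 24 | 24 | 0 |

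So up to the earliest possible opening nothing is missed, whether or not the window is empty. The uncovered time is the further lag L from max(R, T12) to the actual opening. L does not depend on whether the window was empty, and the documents do not bound it.

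**2. Illustration of what falls in the lag.** Inputs:

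- n = 12 Cohort 1 subjects (Protocol section 10.2), all assumed to be still under observation.
- L, in weeks: assumed.
- r, all-cause SAEs per subject-year: assumed, the same in both arms, Poisson.

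Expected SAEs μ = n × r × L / 52, and P(at least one) = 1 − exp(−μ).

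For L = 4:

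- r = 0.25: μ = 12 × 0.25 × 4 / 52 = 0.23, P = 21%
- r = 0.5: μ = 12 × 0.5 × 4 / 52 = 0.46, P = 37%
- r = 1.0: μ = 12 × 1.0 × 4 / 52 = 0.92, P = 60%

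Over a range of lags:

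| L (weeks) | r = 0.25 | r = 0.5 | r = 1.0 |
|---|---|---|---|
| 1.5 | 8% | 16% | 29% |
| 4 | 21% | 37% | 60% |
| 8 | 37% | 60% | 84% |
| 12 | 50% | 75% | 94% |

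These count SAEs of any cause and include the 4 placebo subjects. For the 8 MAU868 subjects alone and L = 4, μ = 8 × 0.25 × 4 / 52 = 0.15 (P = 14%) to 8 × 1.0 × 4 / 52 = 0.62 (P = 46%).

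**3. Do other provisions require the same check?**

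- Pause rule (Protocol section 3.3.1): the SSRC must review after 2 or more treatment-related SAEs, or 2 or more related events in its other categories. A single related SAE, or several judged unrelated, does not trigger it.
- SAE reporting within 24 hours (section 9.3.1): reports go to the CRO's safety group. The section does not call for SSRC assessment.
- Criterion 3: no review date or data cut is stated in the Protocol; timing is left to the DSMB charter.
- Unblinded interim analysis of Cohort 1 (Synopsis and section 10.8.6): it follows completion of treatment and is separate from the review that opens Cohort 2.

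**The case against.** A reader might infer more than the text supports. If subjects 10 to 12 enrol within about 12 weeks of subject 9, the window closes before it opens, and it is tempting to conclude that Cohort 2 would then start on outdated data. The timeline shows the reverse. In that case the full review comes after the 12th randomisation, so it is the latest event and no top-up is needed at that point. The chance of an empty window (16%, 52%, 91% and 99% at assumed Poisson enrolment of 0.5, 1, 2 and 3 subjects a month) is therefore the chance of the favourable ordering and does not measure harm.

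Other safeguards are real. The DSMB condition is a separate requirement for opening, the DSMB sees unblinded cumulative data, and under SAP section 4: "At any time, the DSMB may temporarily suspend enrollment until any significant safety concerns are resolved or terminate the study". Investigators assess causality for every adverse event (section 9.1.3), serious unexpected reactions are reported on an expedited timetable (section 9.5), and a single treatment-related SAE already ends study drug for that subject (section 3.3.2). The criteria open screening, not dosing. The 6750 mg dose corresponds to 100 mg/kg at 67.5 kg, the highest dose in the first-in-human study, where single doses were reported as well tolerated (sections 1.4.1 and 1.6).

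Most of this stands, and it is why the point is minor. It would also be going too far to say that no DSMB review need precede Cohort 2. The charter may schedule one, and it is not among the documents. Likewise, nothing shows that SAEs reported before the SSRC meets would be left out of its review; the Protocol simply names no data cut-off. What the objection does not supply is any provision that makes the SSRC look at SAEs reported between the end of the window and the opening.

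**Conclusion.** The point holds as a low-severity defect in the wording of criterion 2. The SAE update is tied to the wrong closing event. Whether or not the window is empty, SAEs reported after the later of the review and the 12th randomisation, and before Cohort 2 opens, fall outside the assessment the SSRC must make.

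For an assumed 4-week lag and 0.25 to 1.0 SAEs per subject-year in 12 subjects, the chance that at least one SAE falls there is about 21% to 60%. Lag and rate are both assumptions. The figure counts all causes and both arms, so it overstates the chance of missing an event caused by MAU868. If Cohort 2 opens on the day the later of the two events occurs, and the review is current to its date, the gap is zero. The documents do not support a claim that Cohort 2 will start on outdated data, or that such SAEs would go unassessed by everyone.

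**What to change.** In criterion 2, in both the Synopsis and section 3.1 of the Protocol, change the period of the SAE update so that it reads: *after the data cut-off of the SSRC review and before Cohort 2 is opened for screening*. This replaces the span from the SSRC review to randomisation of the 12th subject. Ending the window at the opening closes the gap by construction, including in an expanded cohort. Starting it at the cut-off is a precaution: if the cut-off is the review date, it changes nothing.

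The cost is one sentence in two places and an SSRC check of an SAE line listing at opening. SAEs are already reported within 24 hours, so no extra subjects, visits or procedures are needed. The downside is a possible delay of days if a new SAE needs review. Criterion 3 can stay as it is: DSMB timing belongs to the charter, and requiring an unblinded DSMB package to the same cut-off would add real work.

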DNA	Deoxyribonucleic acid
DSMB	Data Safety Monitoring Board
EC ₅₀	effective concentration
ECG	electrocardiogram
EDC	electronic data capture
eGFR	estimated glomerular filtration rate
ELISA	enzyme-linked immunosorbent assay
FDA	Food and Drug Administration
GCP	Good Clinical Practice
GGT	gamma-glutamyl transferase
H2 Blocker	histamine receptor antagonist
HBsAg	hepatitis B surface antigen
HCT	hematopoietic cell transplant
Hr	Hour
IV	Intravenous

Abbreviation	Definition
IB	Investigator's Brochure
ICF	Informed Consent Form
ICH	International Conference on Harmonization of Technical Requirements for Registration of Pharmaceuticals for Human Use
I/E	Inclusion and Exclusion
INR	international normalized ratio
IRB	Institutional Review Board
ITT	intent-to-treat
IVIG	intravenous immunoglobulin
IWRS	Interactive Web Response System
KDPI	Kidney Donor Profile Index
LDH	lactate dehydrogenase
LFT	liver function test
LLN	lower limit of normal
LLOQ	lower limit of quantification
MedDRA	medical dictionary for regulatory activities
Mg	milligram(s)
mITT	modified intent-to-treat
mL	milliliter(s)
mTOR	mammalian target of rapamycin
NOAEL	No observed adverse effect level
PBPK	physiologically based pharmacokinetics
PD	pharmacodynamic(s)
PK	pharmacokinetic(s)
PT	prothrombin time
RAV	resistance-associated variance
RBC	red blood cell(s)
SC	Subcutaneous
SAE	serious adverse event
SAP	statistical analysis plan
SCR	serum creatinine
SD	standard deviation
SGOT	serum glutamic oxaloacetic transaminase
SGPT	serum glutamic pyruvic transaminase
SSRC	Sponsor Study Review Committee

Abbreviation	Definition
SUSAR	suspected unexpected serious adverse reaction
TEAE	treatment emergent adverse event
ULN	upper limit of normal
ULQ	upper limit of quantification
VP	viral protein
WBC	white blood cell(s)
WHO	World Health Organization

1 INTRODUCTION AND BACKGROUND INFORMATION

1.1 BKV Infection and Nephropathy

The human polyomavirus BK (BK virus or BKV) is a DNA virus that infects 80-90% of the world's population (Kean 2009; Boothpur and Brennan 2010; Egli et al 2009). It is generally acquired during childhood and, subsequently, establishes a lifelong infection in renal tubular and uroepithelial cells (Antonsson 2010). Although the primary and persistent infections are generally clinically silent, BKV reactivation may occur in the setting of organ transplantation when innate immune T cell immunity is compromised by immunosuppressive drugs (Ambalathingal 2017). In particular, recipients of kidney transplant may develop nephropathy and recipients of hematopoietic stem cell transplants may develop hemorrhagic cystitis.

BKV replication in immunosuppressed kidney transplant recipients follows a well-established clinical course from viruria (~35% of all kidney transplant recipients) to viremia (~11%) to nephropathy (3-5%; Sawinski and Goral 2015; Hirsch et al 2013; Dharnidharka et al 2011). The median onset of detectable viruria is 5 weeks post-transplantation (range 2 to 41 weeks), and the median onset of viremia is 10 weeks (range 5 to 51 weeks; Babel et al 2009). The median onset of BKV nephropathy is 42 weeks post-transplantation (range 7 to 113 weeks; Hirsch and Steiger 2003).

Patients who develop BK viremia irrespective of whether biopsy confirms BKV nephropathy have been reported to have significantly lower allograft survival at 10 years (24.8% vs 85.6%, $P < 0.001$; Moura et al 2017). By contrast, patients without viruria do not develop viremia; likewise, patients without viremia do not develop nephropathy (Babel et al 2009).

The main risk factor for BKV replication and the development of disease is the level of immunosuppression, including the type of induction therapy used prior to transplantation. A number of other risk factors including recipient age, male sex, allograft rejection, degree of human leukocyte antigen mismatching, length of cold ischemia time, and recipient and donor BKV serostatus (e.g., donor positive-recipient negative) have also been implicated (Sawinski and Goral 2015). No single risk factor is reliably predictive.

Current treatment guidelines recommend reduction of immunosuppression to control the infection, typically when BK viremia is $> 10^4$ copies/mL (KDIGO Clinical Practice Guideline 2009). Clearance of the viremia takes months and often requires multiple stepwise reductions in the immunosuppression. Subjects for whom immunosuppression is reduced have an increased risk of acute allograft rejection (Bohl and Brennan 2007; Sood et al 2012).

There are no specific or effective anti-BKV therapies. These data underscore the need for more effective means to control or prevent BKV reactivation. MAU868 has the potential to be a safe and well-tolerated therapy that can eliminate a threat to the survival of the renal allograft and greatly simplify the post-transplantation care of kidney transplant recipients.

1.2 MAU868

BKV encodes only seven proteins and lacks the traditional targets for antiviral drugs (e.g., protease, polymerase). The non-enveloped icosahedral virion of BKV is composed of three different viral proteins (VP1, VP2, VP3), but only VP1 (the major viral capsid protein) is exposed on the virion surface.

MAU868 is a human monoclonal antibody (IgG1) that binds the viral capsid protein, VP1, that is responsible for binding to the surface of host cells (i.e., the first step in the infection of new cells; [Tsai and Qian 2010](#)). MAU868 neutralizes all four BKV genotypes at sub-nanomolar concentrations *in vitro*. It recognizes a conformational epitope on VP1 that is highly conserved, resulting in a high barrier to resistance *in vitro*. It is being developed for the prevention of clinically significant BKV infection in immunosuppressed populations, notably solid organ and HCT recipients.

The most relevant data for the present study are summarized in the sections below. For detailed information, please refer to the MAU868 Investigator's Brochure.

1.3 Non-clinical Data

The non-clinical evaluation of MAU868, a human monoclonal antibody recognizing a non-human antigen, was performed according to the ICH S6(R1) guidelines. Details regarding all non-clinical studies conducted to date with MAU868 are provided in the Investigator's Brochure.

No genotoxicity or reproductive toxicology studies were conducted because MAU868 1) is a fully human monoclonal IgG1 antibody comprising native non-modified amino acids, 2) does not contain any chemical linkers or chelators, 3) is highly specific for an epitope unique to human polyomaviruses BK and JC, and 4) there are no pharmacologically relevant animal models.

Because MAU868 is a protein comprised of native amino acids and because if its pharmacological mechanism of action it is considered to be non-genotoxic.

BKV VP1 is the major viral capsid protein and the only protein exposed on the virion surface. Binding of VP1 to ganglioside receptors on the host cell surface initiates internalization of the virus ([Tsai and Qian 2010](#)). Binding of MAU868 to VP1 blocks these interactions and prevents infection of new cells.

MAU868 has picomolar affinity for BKV VP1 and sub-nanomolar neutralization potency against all four BKV genotypes.

Table 2. MAU868 Binding Affinity and Neutralizing Activity

GENOTYPE	Kd (pM)	EC ₅₀ (nM)	EC ₅₀ (µg/mL)
Genotype I	5.8 ± 1.8	0.062 ± 0.068	0.009 ± 0.010
Genotype II	2.8 ± 0.6	0.278 ± 0.175	0.040 ± 0.025
Genotype III	8.4 ± 3.7	0.645 ± 0.397	0.093 ± 0.057
Genotype IV	4.1 ± 1.3	0.143 ± 0.135	0.021 ± 0.020

MAU868 binds to a conformation-dependent epitope on VP1. The key contact residues (Y169, R170, and K172), all located within the VP1 EF loop, are 100% conserved among reference isolates and 156 (genotype I) and 66 (genotype IV) GenBank sequences analyzed. Mutations at these locations confer either a loss of viral fitness (i.e., inability to replicate) or no change in susceptibility to MAU868.

Resistance selection experiments in renal proximal tubule epithelial cells infected with BKV genotype I and genotype IV, which comprise 95% of global seroprevalence, failed to generate virus with genotypic resistance to MAU868 after six serial passages (>84 days in cell culture). Mutant BK viruses harboring a series of VP1 polymorphisms at other locations in VP1 that were identified through analyses of available sequences in GenBank also confer no reduced susceptibility to MAU868 *in vitro*. The available non-clinical data demonstrate a high barrier to the development of resistance to MAU868 *in vitro*.

Repeated dose-toxicity studies were conducted in rats. Once weekly IV or SC administration for 4-weeks (5 doses total) of MAU868 up to 750 mg/kg IV and 150 mg/kg SC to rats was well tolerated. The NOAEL for IV administration was 750 mg/kg/week; the NOAEL for SC administration was 150 mg/kg/week.

